#### Pilot subjects:

The first 2 subjects will be pilot subjects to review standard procedures. Dosage of the medication, side effects, cue-induced cravings assessments, and safety protocol will be carefully evaluated to ensure that all risks are minimized for our participants. Data from pilot

subjects will be especially critical for fine-tuning the baseline cue-reactivity assessment, in that we want to ensure participants will be sufficiently reactive to cues at baseline. If the pilot subjects show insufficient baseline cue-reactivity, one potential modification would be the development of more appropriate evocative cues.

#### Potential difficulties:

- *Insufficient recruitment:* The director of the BWH Bridge Clinic is a collaborator to help identify potential subjects. The PI directs the BWF Addiction Recovery Program that treats OUD with buprenorphine. Together there are over 200 active patients with OUD in those programs receiving buprenorphine. As such, we are confident in the ability to recruit a sufficient number of subjects to complete the study in the proposed timeline. Nevertheless, we will also recruit potential subjects using Rally (rally.partners.org), and internet advertisements such as Craigslist. In total, we expect to screen 25-30 patients per month with these strategies, enrolling at least 5% of those we screen, leading to the target enrollment of 10 subjects in 8 months.
- *Insufficient baseline cue-reactivity:* Cue-reactivity among OUD patients taking buprenorphine for at least one month is not known. Prior studies have demonstrated that OUD patients stabilized long-term on methadone remain cue-reactive, but at lower levels. In the study by one of the consultants to this project ([name]), subjects taking buprenorphine for detoxification (i.e. for a few days) were sufficiently reactive to cues. As such, in order to ensure enrollment of subjects who are cue-reactive, we will enroll subjects who have been stable for at least a month, but not more than one year of treatment. We believe this will ensure enrollment of the most homogenous population of subjects who are sufficiently reactive to cues. In addition, we will evaluate cue-induced anxiety (on a visual analog scale of 0 to 10) concurrently, which will provide valuable information about the impact of CBD even if subjects do not respond with cravings to cues.

- *Sex differences in cue-reactivity:* Prior research has indicated that females may be more reactive to cues. Our pilot study will not be powered to detect sex differences. Nevertheless, based on the results of this study, future studies can be powered sufficiently to account for sex differences in cue-reactivity.

## VI. Biostatistical analysis:

Our primary interest in this pilot study is in estimating the effect sizes and variance in the outcomes to inform the design of a larger randomized trial. We will calculate the effect size representing the magnitude of change over time in the cue-reactivity score, defined as the difference in scores between heroin-related and neutral cues. The primary outcome is the change in cue-induced craving from pre-exposure to post-exposure. If the change in cravings is normally distributed, then a paired-samples t-test will be used to examine the statistical significance of the change in cue-induced craving. Accounting for the possibility of reduced cue-reactivity for participants taking buprenorphine compared to those not taking any medications, the estimated mean change in cue-induced cravings scores from prior studies is -1.5 (SD 1.5). Based on this estimate, and a conservative estimate of a correlation of  $r=0.60$  between the two time points, a sample size of 10 is needed for 88% power and two-tailed alpha set at 0.05 for a paired-samples t-test. A point estimate of the difference in the change and the 95% confidence interval will be reported. Conversely, if the change in cravings is not normally distributed, then a sum rank test will be used.

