**III. Subject Selection:**

The proposed study is a single-arm, open-label feasibility pilot. The study will enroll 12 adult subjects (including 2 pilot subjects) with OUD currently receiving treatment with buprenorphine or methadone.

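### The fallback for a paired, single-arm primary outcome is called a sum rank test; read literally this is a test for two independent groups, and the Wilcoxon signed-rank test should be named instead

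*Combined protocol and SAP*

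**What the plan says.** Section III (Subject Selection) fixes the design: "The proposed study is a single-arm, open-label feasibility pilot". Section VI builds a cue-reactivity score, "defined as the difference in scores between heroin-related and neutral cues", and states that "The primary outcome is the change in cue-induced craving from pre-exposure to post-exposure". Each subject therefore contributes one number, a within-subject change.

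If that change is normally distributed, "then a paired-samples t-test will be used to examine the statistical significance of the change in cue-induced craving". The sample size is justified for this test only: with a mean change of -1.5, an SD of 1.5 and a correlation of 0.60 between the two time points, "a sample size of 10 is needed for 88% power and two-tailed alpha set at 0.05 for a paired-samples t-test". An interval is promised without a stated method: "A point estimate of the difference in the change and the 95% confidence interval will be reported".

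The last sentence of the section gives the other branch: "if the change in cravings is not normally distributed, then a sum rank test will be used". The fallback is named nowhere else in the document, and no other sentence calls it signed-rank, Wilcoxon or paired.

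**The concern.** The nonparametric counterpart of the paired t-test is the Wilcoxon signed-rank test. The name in the plan is closest to the Wilcoxon rank-sum test, a different standard test that needs two independent samples. There are two ways to apply it literally, and neither fits:

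- **On the change scores.** There is one set of changes and no second group, so the test cannot be run.
- **On pre scores against post scores.** The test runs, but it treats ten pairs as twenty unrelated observations and ignores the correlation that the sample-size calculation relies on.

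What is at stake is the p-value for the primary outcome when the fallback is reached. With ten subjects the two tests can easily fall on opposite sides of 0.05. A pre-specified rule should not leave the choice between them open until the data are seen.

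**Working it through.** **Inputs, all from section VI.** N = 10; mean change -1.5; SD 1.5; correlation r = 0.60; two-sided alpha 0.05.

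**1. Reproduce the stated power.** Read 1.5 as the SD at each visit.

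- SD of the change = 1.5 × √(2 × (1 − 0.60)) = 1.342
- Standardised change = 1.5 / 1.342 = 1.118
- Noncentrality = 1.118 × √10 = 3.54, on 9 degrees of freedom
- Power from the noncentral t = 88.1%, which matches the stated 88%

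If 1.5 is instead the SD of the change, the standardised change is 1.0 and power is 80.3%. The stated figure therefore depends on the pairing through r = 0.60.

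**2. What ignoring the pairing does.** The variance of the mean change is 2 × 1.5² × (1 − 0.60) / 10 = 0.18. Treating the visits as independent gives 2 × 1.5² / 10 = 0.45, which is 2.5 times too large. A test calibrated to the larger variance rejects too rarely.

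**3. Test against test.** Simulation of bivariate normal scores, SD 1.5 per visit, n = 10, mean change -1.5 for power and 0 for type I error, 100,000 runs per cell. Exact two-sided critical values were used: signed-rank W ≤ 8 (actual level 4.88%) and rank-sum U ≤ 23 (4.33%).

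| r | Power, rank-sum | Power, signed-rank | Type I error, rank-sum |
|---|---|---|---|
| 0.8 | 57% | 99% | 0.05% |
| 0.7 | 55% | 94% | 0.2% |
| **0.6** | **53%** | **87%** | **0.5%** |
| 0.5 | 53% | 79% | 0.9% |
| 0.3 | 51% | 64% | 1.9% |
| 0 | 51% | 50% | 4.4% |
| -0.3 | 51% | 40% | 7.1% |

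Signed-rank type I error is 4.8% to 5.0% throughout. Repeat simulations agreed to within about one percentage point. At r = 0.60, 33.6% of simulated trials are significant by signed-rank only and 0.6% by rank-sum only. If 1.5 is the SD of the change, with r = 0.60, power is 42% for rank-sum and 79% for signed-rank.

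**4. The whole two-step rule.** The plan names no normality check, so Shapiro-Wilk at 0.05 is assumed. With normal data about 5% of trials then reach the fallback. At r = 0.60, overall power is about 86.6% with rank-sum as the fallback and 88.0% with signed-rank, a loss of about 1.5 points before rounding. Type I error is 4.7% against 5.0%. Over r from -0.3 to 0.8 the effect on power runs from a gain of 0.6 points to a loss of 2.2.

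**5. Non-normal data.** The document gives no distribution, so no general figure can be claimed. In one assumed skewed case (lognormal margins, pure location shift, r = 0.60 on the underlying normal scale), power was similar, about 86% for rank-sum and 84% for signed-rank, but rank-sum type I error was still about 0.5%.

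**The case against.** The strongest reply is that the sentence rules out the harmful reading. The fallback is applied to the change, one value per subject, as the alternative to a paired t-test in a single-arm study. To run a rank-sum test an analyst would have to set that endpoint aside and treat the two visits as separate groups. The phrase used is not a standard test name, and the signed-rank statistic is itself a sum of ranks. On this view the text is merely imprecise.

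Three further points carry weight. The 53% against 87% comparison assumes normal data, whereas the fallback is meant for non-normal data. The simulated scores are continuous and unbounded, while ratings are on a 0 to 10 scale and section V (Potential difficulties) anticipates that cue-reactivity may be low; ties and zero changes are plausible and are not modelled. And section VI puts estimation of effect sizes and variance ahead of testing.

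Most of this stands, and it is why the point is minor. A slip is the likeliest explanation, and the test-against-test figures only illustrate the mismatch. It does not remove the defect. The section still plans a significance test, and the nearest standard test to the one named either cannot be run on the change scores or discards the pairing. No other sentence settles which test is meant.

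**Conclusion.** The concern holds as a minor error in the primary analysis rule. The fallback, read by its nearest standard name, does not fit a paired single-arm design.

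If a rank-sum test were run on pre against post scores, it would be conservative at any positive correlation between visits. The power gap shrinks as r falls and is gone at r = 0; at negative r, which is unlikely here, the type I error exceeds 5%. The practical effect is confined to trials that reach the fallback: about 1.5 points of overall power under normality, given r = 0.60 and the assumed Shapiro-Wilk check. Under non-normality the effect is unknown and could be larger or reversed.

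The 88% power, the sample size of 10, the primary t-test and the effect-size estimate are not affected.

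**What to change.** In the last sentence of section VI, replace the named fallback with *the Wilcoxon signed-rank test on the within-subject change in cue-induced craving*. If a confidence interval is reported alongside the fallback, it should also be a paired one; the Hodges-Lehmann interval that corresponds to the signed-rank test is one option.

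The cost is one sentence. Data collection, sample size and participants are unaffected.

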## VII. Risks and discomforts

The well-being of the study participants is of utmost importance. The in-depth screening procedure has been designed to ensure that individuals with any underlying medical or psychiatric illness are identified that may place them at greater risk for experiencing adverse effects during the study. The protocol raises several areas of concerns: confidentiality, emotional distress, adverse reactions to cue-exposure, suicidal ideation, cannabidiol medication, buprenorphine medication, and cue-reactivity safety.

**Confidentiality:** Confidentiality is of utmost importance given the sensitive nature of the illness and data collected. During research there is always a possibility for a breach of confidentiality, which may potentially cause personal, social, occupational, legal, and other harm. Our research team is very aware of the importance of maintaining strict confidentiality and has prior experience dealing with sensitive information. The following precautions will be used to protect the privacy of participants and maintain confidentiality of research data: all staff will be trained in confidentiality and data security procedures; privacy will be maintained by conducting all study procedures in private hospital rooms or in close, sound-proof rooms; data will be de-identified and coded with unique ID numbers; data will be securely stored in locked filing cabinets in locked rooms; electronic data will be stored in password protected documents located on password protected computers and secure servers; the key linking participants names and ID numbers will be stored in a separate password protected document in a password protected computer; access to data storage areas will be restricted to authorized study personnel; and all analysis will be conducted on de-identified data. While breach of confidentiality is possible, these safeguards will ensure that such a breach will be highly unlikely.

**Emotional distress:** Some patients may experience discomfort or embarrassment related to providing urine samples or answering questions about substance use and other personal behaviors. They could also experience unexpected encounters with friends or associates while in the study. However, based on prior studies with this population, we expect

the degree of distress to be very limited. All research personnel will be extensively trained on study procedures, including the conduct of the interviews that elicit personal information, and the importance of being sensitive to and respectful of all participants. In cases where emotional distress does occur, research personnel will be trained on how to identify and address it, and when to terminate an interview. Multiple levels of back-up support for research personnel will be developed. The candidate is a board certified psychiatrist, and will be able to ensure that appropriate services are received.

**Adverse reactions to cue-exposure:** The cue exposure procedure will end with a standardized relaxation and debriefing exercise. Before participants are discharged from each study session, their well-being will be assessed by the study staff and a standardized safety and adverse events questionnaire will be used to assess any adverse events. If needed, participants will be referred for further clinical evaluation and assistance. It is important to note that cue-exposure is a safe paradigm for studying craving in this population when employing debriefing procedures.

**Suicidal ideation:** Patients with OUD frequently have psychiatric co-morbidities, namely depression. Participants who disclose any suicidal ideation during the study (either through spontaneous expression of suicidal ideation, or self-reported on the M.I.N.I. screen or the PHQ-9) will result in emergent evaluation by a licensed clinician member of the study staff for appropriate assessment and triage. Any disclosures will be handled within existing legal mandates, clinical practice, and social norms. Consistent with standard clinical practice, when possible, disclosures will be discussed with the participant to determine the best management options. This may include notifying the outpatient providers or family members, referring to medical treatment, calling emergency services, or escorting the participant to the Emergency Room at Brigham and Women's Hospital. When required by law, the police department will be notified. The candidate is a board certified psychiatrist and has extensive experience managing acutely distressed patients with mental or substance use disorders.

**Cannabidiol medication safety:** All subjects in this pilot trial will receive 600mg of cannabidiol for 3 consecutive days. Cannabidiol (Epidiolex) is approved by the U.S. Food and Drug Administration (FDA) for the treatment of seizures associated with two rare and severe forms of epilepsy. However, cannabidiol is not approved by the FDA for treatment of opioid use disorder. This protocol has been reviewed by the Center for Drug Evaluation and Research at the Food and Drug Administration to determine whether it meets the regulatory criteria for an exemption from the requirement for the submission, and we received the FDA IND exemption letter November 13, 2019. Although this proposed clinical evaluation is for an "off-label" indication of cannabidiol, it does not involve a route of administration or dosage level or use in a patient population or other factor that significantly increases the risks (or decreases the acceptability of the risks) associated with the use of the Epidiolex (cannabidiol). The proposed dose is within FDA-approved mg/kg maximum daily dose limits. There are now two randomized placebo-controlled studies of administering 400mg or 800mg of cannabidiol to participants with opioid use disorder with no adverse effects. Nonetheless, cannabidiol may cause participants to experience side effects such as: somnolence; decreased appetite; diarrhea; transaminase elevations; fatigue, malaise, and asthenia; rash; insomnia, sleep disorder, and poor quality sleep; infections; and suicidal thoughts or actions. All participants will be told of these potential side effects, and the screening procedures, including liver function tests, are in place to minimize these potential risks. The principal investigator will continually assess and monitor adverse effects both during and after cannabidiol administration, as noted in the Schedule of Measures.

**Buprenorphine medication safety:** All subjects in this pilot trial will be stable on buprenorphine prior to enrolling, and were thus previously deemed appropriate for the medication by their buprenorphine-waived physician. Buprenorphine has been tested extensively and is FDA-approved for the treatment of OUD. Indeed, medication-assisted

treatment (with buprenorphine, methadone or naltrexone) is the standard of care for the treatment of OUD. Because buprenorphine is a partial mu-opioid agonist, the medication can in some individuals cause intoxication, especially if used intravenously. As such, only the combination tablet that contains naloxone will be used, unless the participant has a documented allergy to naloxone. The combination tablet will produce a clinically significant opioid withdrawal if injected. All participants will be told of this reaction, and will also be asked to refrain from injecting the medication. Buprenorphine can also cause a mild euphoria and respiratory depression, but much less than compared to full agonists. The candidate has extensive experience managing OUD patients with buprenorphine, and is well versed in the appropriate clinical management of any emergent side effects from buprenorphine. Subjects will also be advised that ingesting buprenorphine with other sedative drugs, such as benzodiazepines, dramatically raises the possibility for a synergistic reaction that can cause an overdose or even death. Individuals with any underlying liver disease or have a history of hepatitis C will be informed that buprenorphine use has been rarely associated with liver failure, and that liver function test will be obtained. Subjects will be informed that buprenorphine medication should be stored in a secure location, ideally with a lock-box, to ensure no one else can access the medication including children.

**Cue-reactivity testing safety:** The risks associated with the proposed study are minimal. It is hypothesized that participants may experience mild to moderate and transient opioid craving in response to images. All participants will be currently in stable treatment with sublingual buprenorphine. Nonetheless, if a participant experiences more than mild to moderate distress at any time during the study, he or she will be given the option to discontinue participation and to meet with a research staff member. Study staff will conduct informal assessment of craving following completion of the study and if the distress persists, the principal investigator will be notified to determine whether further assessment is indicated. [name] is extensively trained in managing patient in acute distress.

**Pressure pain and temporal summation of pain testing:** All procedures will be performed only with the approval of Partners Human Research Committee. Written informed consent will be obtained from every subject by one of the study team members. We will demonstrate the nociceptive testing during the consent process, performing the procedure in front of potential subjects, and offering participants the option to discontinue quantitative sensory testing at any time. There is a slight chance of mild transient bruising associated with use of the algometer. In our experience with previous studies, this is quite rare (< 5 % of cases). No skin breakage has been observed by investigators in previous studies or reported in literature with the specially machined pinprick probes. Despite not breaking the skin, all pinprick probes will be disinfected in a 10% bleach solution between participants. Both QST measures (pressure algometer and pinprick probes) will be demonstrated to the patient on study staff as part of the informed consent process.

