**Inclusion criteria:**

- Diagnosis of DSM-5 opioid use disorder, severe
- Currently in treatment with methadone or buprenorphine

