**IV. Subject enrollment:**

Adults with a DSM-5 diagnosis of OUD and who are currently in treatment with buprenorphine or methadone will be recruited. Inclusion and exclusion criteria are listed above, which are designed to favor internal validity given the preliminary nature of this trial, and to recruit as homogenous of a group of subjects as possible. Patients with OUD at Brigham and Women's Hospital (BWH) and Brigham and Women's Faulkner (BWF) Addiction Recovery Program (ARP) will be recruited via Patient Gateway for possible inclusion. Subjects will also be recruited from the Partners Clinical Trials website, <http://Rally.partners.org>, as well as print advertisements and flyers, which will also be distributed to local methadone and buprenorphine clinics. Subjects will also be recruited via automated IRB-approved recruitment emails sent from their providers at BWH Bridge and/or BWFH ARP through the "Patient Gateway Blast." All study visits will be conducted at the BWH Center for Clinical Investigation. Study staff will perform a preliminary screen to establish suitability for the study. If suitable, a study staff will obtain informed consent and apply the inclusion and exclusion criteria. If the subject meets the full inclusion and exclusion criteria, the subject will be enrolled. Subjects will not be enrolled from among the Investigator's own patients as the Principal Investigator is no longer seeing any patients clinically.

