**Schedule of visits and assessments:**

The blood and urine samples (see **Table**

**1**) collected during the Baseline Visit 1 and Post-Exposure Visit 3 will be used only for inclusion/exclusion purposes.

Specifically, participants who are currently pregnant (as confirmed by the pregnancy test), have hepatic liver enzymes greater than three times the upper normal limit (as confirmed by the liver

function tests, or LFTs), or who are not taking their buprenorphine as clinically prescribed (as confirmed by the urine toxicology) will be excluded. Other inclusion/exclusion criteria not dependent on blood and urine samples are detailed elsewhere in this protocol. Baseline measures and the pre-exposure cue-induced cravings, anxiety, and pain assessments will both be conducted before the CBD administration. The first oral CBD administration will occur during Visit 2, following the pre-exposure assessment. Participants will be instructed to take the second and third oral CBD doses at home, and will be asked to complete a drug diary which will also assess general craving and adverse effects. Participants will be asked to take their regular dose of sublingual buprenorphine at their regular time, and to return to the BWH Center for Clinical Investigation for Visit 3 following their last home administration of oral CBD. Follow-up assessments, including post-exposure cue-induced cravings, anxiety, and pain assessments, will occur after administration of CBD. During Visits 2 and 3, general craving, anxiety, and pain scales will also be administered before the cue-reactivity paradigm. There will also be continuous physiological monitoring (vital signs: heart rate, blood pressure, respiration rate, oxygen saturation, and temperature) during Visits 2 and 3. Table 1 summarizes the schedule of visits and assessments.

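### Methadone patients are eligible and recruited, but the adherence exclusion, the dosing instruction and the sedative and storage advice are written for buprenorphine only

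*Combined protocol and SAP*

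**What the plan says.** Methadone patients are plainly part of the study. The aim in Section II and the enrolment statement in Section III cover treatment with either drug. The inclusion criterion reads "Currently in treatment with methadone or buprenorphine". Section IV has flyers "distributed to local methadone and buprenorphine clinics".

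Section VII is written for a different population. Under buprenorphine medication safety it says "All subjects in this pilot trial will be stable on buprenorphine prior to enrolling", and under cue-reactivity testing safety it says "All participants will be currently in stable treatment with sublingual buprenorphine".

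Four instructions name buprenorphine alone:

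- **Adherence exclusion** (Section V, schedule of visits and assessments): participants "who are not taking their buprenorphine as clinically prescribed (as confirmed by the urine toxicology) will be excluded".
- **Dosing instruction** (same place): "Participants will be asked to take their regular dose of sublingual buprenorphine at their regular time".
- **Sedative advice** (Section VII): subjects are warned that "ingesting buprenorphine with other sedative drugs, such as benzodiazepines, dramatically raises the possibility for a synergistic reaction", with overdose or death as the possible result.
- **Storage advice** (Section VII): subjects are told that "buprenorphine medication should be stored in a secure location, ideally with a lock-box".

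**The concern.** The eligibility text and the risk text cannot both be true. If the difference were confined to descriptive sentences it would be editorial. It is not, because an exclusion rule, an instruction to participants and two pieces of safety advice rest on the narrower description.

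Two things are at stake. The first is consistent eligibility. Staff who follow the text have an adherence rule for one of the two eligible treatments and must improvise for the other. The second is safety advice. The protocol itself judged sedative overdose and access by others, including children, serious enough to require advice, but it words that advice for only one of the opioid agonists its subjects may be taking.

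**Working it through.** No arithmetic applies. The plan gives no figure on this point, and its sample-size calculation does not enter into it. The check is a comparison of texts.

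**Step 1. Who can be enrolled.** Sections II, III and IV each name both drugs. Section III sets 12 subjects, including 2 pilot subjects, and does not limit how many may be on methadone.

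**Step 2. What each measure does for each kind of subject, read literally.**

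| Measure | Subject on buprenorphine | Subject on methadone |
|---|---|---|
| Urine-toxicology adherence exclusion (Section V) | Excluded if not adherent | Rule does not apply |
| Keep the regular dose at the regular time (Section V) | Instructed | Instruction names another drug |
| Sedative-overdose advice (Section VII) | Advised | Advice names another drug |
| Secure-storage advice (Section VII) | Advised | Advice names another drug |

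**Step 3. Whether a methadone version appears elsewhere.** It does not. The exclusion list in Section III has no adherence criterion for either drug, so Section V is the only place where adherence is made a condition. Section VII has a paragraph on buprenorphine safety and no counterpart for methadone. Its one mention of methadone is in a general sentence on the standard of care.

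**Step 4. Whether the buprenorphine reassurances carry over.** Section VII relies on four: earlier clearance by a physician waived to prescribe buprenorphine, partial agonism, a combination tablet with naloxone, and less respiratory depression than with full agonists. Each is argued from buprenorphine or its formulation. None is offered for methadone, so the section contains no risk assessment for that drug.

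**Step 5. Whether other safeguards do the same work.**

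- The withdrawal scale (COWS) and the Timeline Followback are listed in Table 1, though their visit marks did not survive in the text available. Neither is stated to check methadone adherence.
- The drug diary is described as covering general craving and adverse effects, not agonist dosing.
- Vital signs, including oxygen saturation, are monitored at Visits 2 and 3, while CBD doses 2 and 3 are taken at home.
- An adverse-events questionnaire is completed before discharge from each session.
- The exclusion of drugs with important pharmacokinetic interactions with CBD is generic and does not name methadone.

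These reduce the practical risk. None is stated to do what the four measures do.

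**The case against.** The strongest reply is that this is unfinished editing with little consequence. Other parts of the protocol also speak of buprenorphine alone (the background, the timeline, the potential difficulties and the potential benefits), which fits text written for one drug and later widened. Every subject is already under a treatment programme that prescribes the agonist. Patients who need more than outpatient care for sedative use are excluded. The urine panel may already detect methadone, in which case the adherence gap is one of wording. Advice on sedatives and storage reaches subjects largely through consent, and those pages were not available.

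Much of this stands, and it limits how far the point can go. It does not remove it. An exclusion rule and a dosing instruction are applied as written, and advice in the consent form would repair neither.

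A reader might infer three stronger things, and the documents support none of them:

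- **That methadone subjects go unadvised.** The consent form may advise them. Only the protocol text can be judged.
- **That CBD makes the sedative interaction worse.** Section VII lists somnolence among CBD's side effects, but nothing in the documents shows an added interaction.
- **That the primary outcome is biased by methadone dose changes.** The design is an uncontrolled before-and-after comparison, so the thought is natural. With 10 subjects, a shift of x points in one of them moves the mean change by x/10, but that is true of any outlier from any cause, and the documents give no value of x for a missed or changed dose. Nor can a direction be claimed. The remark in Section V on lower cue-reactivity concerns patients stabilised on methadone for a long time and says nothing about a single dose.

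**Conclusion.** The point holds for the protocol text. Methadone patients are eligible and recruited, two statements say that all subjects take buprenorphine, and four operative measures follow those statements. Taken literally, the adherence exclusion and the dosing instruction miss a methadone subject, and the protocol's sedative and storage advice names a drug that subject does not take.

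No size of harm or bias can be given. The number of methadone subjects is not stated (anywhere from 0 to 12 would fit the eligibility text), and neither is the effect of a changed dose. The conclusion assumes only that the protocol is applied as worded and that the consent form, which was not seen, does not change the eligibility rule. It should be corrected because it touches eligibility and safety advice and the correction is cheap, not because harm has been shown.

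**What to change.** One amendment:

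1. **Section V.** Extend the adherence exclusion and the regular-dose instruction to the prescribed agonist, whether buprenorphine or methadone. Confirm that the urine panel used at Visits 1 and 3 detects methadone.
2. **Section VII, population.** Correct the two statements that all subjects take buprenorphine.
3. **Section VII, advice.** Word the sedative and storage advice for both drugs. Add a short methadone safety paragraph that does not borrow the buprenorphine reassurances, and align it with the consent form.

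The cost is the amendment itself, a matching consent change if the consent form has the same gap, and possibly one added assay, since the contents of the panel are not given. The downside is that methadone patients not taking their dose as prescribed would be excluded, under the rule that already applies to buprenorphine patients.

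A line in the drug diary for the last agonist dose would be a sensible extra for subjects on either drug. It is optional and not part of this defect.
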